#### Planned PPI/E

[name] will coordinate public engagement work with support from the wider team. This builds on previous work and will take the form of two main streams:

- A public partner group drawn from HEPE and interested public partners who were
  involved in the feasibility study will be consulted throughout the project. [name] will host
  structured workshops to obtain feedback on key trial materials, including the project
  website and sign-up process and associated communication tools. [name] will also
  provide feedback on the results of the pilot and planning for next steps.
- Two lay members of the project steering group.

# Equality, Diversity and Inclusion Assessment

# Inclusion of underserved groups

The project is targeted towards people with mild-to-moderate depression and anxiety. We know that some groups may be more at risk of mental ill health, including those from the poorest households, those with long term physical health conditions, people from African-Caribbean communities, and those from LGBTQIA+ communities. We will also consider place-based inequalities. We will be offering nature-based interventions in three localities in the South West: Wildfowl and Wetlands Trust near Bridgwater Somerset, Eden close to St Austell Cornwall, and the Sensory Trust in Cornwall. Many coastal communities experience high levels of poverty related distress and suffer from health and wealth inequalities, which can be "hidden" in regional statistics (CMO, 2020). Furthermore, despite apparent availability of green and blue spaces, those from socially deprived areas are less likely to access these. Rural communities may also suffer from access issues and have high levels of need. For example, Bridgwater in

Somerset (close to the Wildfowl and Wetlands Trust site) contains the most deprived wards in Somerset, with nearly two-thirds of households experiencing deprivation according to at least one of the four metrics in North Bridgwater (ONS census data 2021).

We will work closely with our nature-based provider partners to identify suitable local community and social media groups through which our pilot RCT can be advertised to try and ensure that a diverse participant population is recruited. Use of inclusive language and images will be supported. The process evaluation will assess how well these strategies work. We will also work closely with nature-based providers to understand how activities and access may affect accessibility for people with health conditions or impairments, encourage adaptations where feasible, and provide clear guidance to potential participants in recruitment material where adaptations may not be possible

Those with serious or complex mental ill-health will not be able to participate due to the type of support available from the nature-based providers. We will use an online screening tool (also used in the feasibility study, IRAS317076) for interested people and those scoring high on the PHQ9 or GAD7 will not be able to participate in the RCT. Instead, they will be directed to appropriate alternative sources of support. If people are unable to navigate the online mood screener or need help understanding and answering the questions, they will be able to email, text or call a member of the research team who will help them to work through the screener questions. The contact details will be highlighted on the screening pages. This support will be available throughout the duration of the recruitment process but primarily during working hours.

Participants will need a good understanding of English to take part in the trial, as all intervention instructions -including safety guidance related to specific activities and tool use - will be delivered in English by the nature-based providers on the day. This requirement will be clearly outlined in the eligibility guidelines. Given the limited capacity of these small VCSE organisations, staff are unable to provide multilingual support or accommodate other languages. Additionally, introducing non-English speakers to a group environment where communication barriers exist could lead to discomfort or feelings of isolation, potentially causing harm. This criterion is not intended to exclude non-English speakers but rather to ensure a safe and ethically sound trial within the current practical constraints.

## Trial Design

GREENGAGE is an external parallel arm, pilot RCT with an embedded qualitative process evaluation. This will compare a nature-based intervention (plus usual care – including medication, talking therapy, other social prescription activities) with a waitlist control arm receiving usual care, using individual 1:1 randomised allocation within each of the 3 locations. The results will inform a definitive fully powered trial.

# **Trial Setting**

This is a multicentre trial, with nature-based activities being offered in three locations in the South West of England:

1. Wildfowl and Wetlands Trust (WWT) near Bridgwater, Somerset.

- 2. Eden Project, near St Austell, Cornwall.
- 3. Sensory Trust, near Falmouth, Cornwall.

#### **Site-Specific Requirements**

Each site is responsible for organising and delivering nature-based activities in accordance with the trial protocol and handbook. These activities will include guided nature walks, conservation tasks, pond dipping, and other therapeutic outdoor activities. Sites must ensure:

- Availability of suitable outdoor spaces for the intervention.
- Accessibility for participants with mild-to-moderate physical limitations.
- Trained facilitators to deliver activities safely and effectively.

#### **Types of Sites and Their Roles**

- Participant Identification Centres (PICs): General practitioners (GPs), link workers, social media platforms, and community flyers will function as PIC sites. These sources will facilitate participant identification by providing study information and directing potential participants to the project website. No research procedures, including consent or data collection, will take place at these sites. A list of the PIC sites, including contact details of GP's, is maintained by the trial management team and available upon request.
- Recruiting Sites: The project website serves as the sole recruiting site for this study. All potential participants will be directed to the website, where they will access the Participant Information Sheet, review eligibility criteria, and provide online consent before completing a screening tool. Those who meet the eligibility criteria will then be enrolled into the study through the website.
- Intervention Delivery Sites: The three nature-based providers listed above will deliver weekly group activities for six consecutive weeks. They will document relevant processes and pathways and engage in a focus group discussion to describe their experiences of being involved in the trial.

#### **Eligibility Criteria for Intervention Delivery Sites and Facilitators**

- **Sites**: Intervention sites must be located within the designated geographical areas and possess the necessary facilities to support group nature-based activities in an accessible and safe environment.
- **Facilitators**: Facilitators must have experience in leading nature-based activities and be trained in participant safety, inclusivity, and first aid. Additionally, they will complete an online training webinar, delivered by the research team, to ensure they understand the study's purpose, as well as their roles and responsibilities within it.

## **Participant Population**

Participants will be adults aged 18+ with mild-to-moderate depression and/or anxiety. These individuals will be identified through primary care settings, such as GP practices, and via community outreach and social media advertisements. Given the prevalence of anxiety and

depression, participants are anticipated to come from both rural and semi-urban areas, including underserved and socioeconomically disadvantaged populations.

#### **Usual Care Pathways**

Participants will typically receive usual care through GPs or mental health services, including medication, talking therapies, or other forms of social prescribing. The trial integrates with these pathways to recruit participants and complement existing support mechanisms. This trial setting reflects the practical considerations of delivering community-based interventions while ensuring access for diverse participant groups.

# Participant Eligibility Criteria

#### Inclusion criteria

- People aged 18 years or over.
- People with mild-to-moderate depression or anxiety, defined by scores of 10 to 19 on PHQ-9 and/or 5-14 on GAD-7. With that, participants can have no/low depression and mild to moderate anxiety, mild to moderate depression and no/low anxiety, or both mild to moderate depression and mild to moderate anxiety.
- Ability to give informed consent to written information sheets and consent forms.
- Participants may be on any current treatment for mild-to-moderate depression and/or anxiety, or none.

#### Exclusion criteria

- People with severe depression and and/or anxiety (as defined by scores of 20 or more on the PHQ-9 and/or 15 or more on GAD-7)
- People unable to understand written and verbal instructions in English
- Those with serious physical impairment that would prevent participation in nature-based activities (such as walking, gardening, pond dipping)
- Severe and enduring mental disorders
- Actively suicidal or psychotic (as assessed by the mood screener see Appendix 1).

# Recruitment and Participant Identification

We aim to recruit 84 participants (42 in each arm) across three nature-based providers: the Wildfowl and Wetlands Trust, the Eden Project, and the Sensory Trust. These participants will be adults (≥18 years old) with mild-to-moderate depression and/or anxiety, defined by scores of 10-19 on Patient Health Questionnaire (PHQ-9) and/or 5-14 on Generalised Anxiety Disorder assessment (GAD-7).

We will use multiple approaches to reflect the plurality of typical access routes, maximise participant numbers and aim to recruit a diverse population into the study. We will recruit via:

- GP practices in each area
- local link workers/ community connectors
- social media (e.g. local Facebook advertisements, nature-based provider accounts and pages)
- flyers in local community venues, MH support groups

In our single-arm feasibility study, we used both GPs and direct recruitment through social media (local Facebook adverts, nature-based provider routes). While initially recruitment through GPs was slow, reflecting winter workload and staff challenges, we recruited 55% of participants through this route in the feasibility study. Each of the three sites will have three local GPs to support recruitment.

GPs and link workers will receive initial information about the research project through an online seminar. They will identify potential participants and direct them to our project website - https://greengage-research.org - to learn more about the study and sign-up if interested. Those recruited via social media or flyers in local community venues will also be directed to our project website.

The GREENGAGE project website will contain further information about the research, detailing our team, the purpose of the trial, our nature-based provider partners, and what to expect from their participation. The project website will also specify the eligibility criteria and will contain the full participant information sheet in addition to the summary version. Interested users will be prompted to provide consent and will complete the screening questionnaires (see Appendix 1), to ensure that they meet the inclusion criteria. Potential participants will be provided with a mobile telephone number to contact a member of the research team ([name]) if they have further questions about the study or need support completing the questionnaires during working hours.

If potential participants do not meet the criteria and have more serious/complex mental ill health, they will be notified immediately, and the online screening tool will direct people to a range of alternative support appropriate to the level of need (see Appendix 1). This approach was used successfully previously in our feasibility study.

# Randomisation and Blinding/Allocation Concealment

The randomisation process will be set up and tested by the trial statistician. Participants will be randomly allocated (using computer generated random numbers) to the intervention or control group, in a 1:1 ratio stratified by location. The aim is to recruit 28 participants at each of the three locations. Within each location, participants will be randomised in two batches of 14, with seven participants allocated to each trial arm per batch. The seven participants in the intervention arm of a given batch will form the group within which they undertake the intervention. As part of this pilot RCT, one key objective is to assess the speed of recruitment. The maximum time we are willing to wait to recruit 14 participants per batch will be reviewed and discussed in team meetings. Currently, it has been decided that a batch will proceed with no fewer than twelve participants (assuming two could drop out, leaving four in an intervention group). However, the specific time frame for reaching this minimum threshold has yet to be determined.

For each batch, the trial manager will provide the statistician with a list of unique, non-identifying participant numbers to maintain allocation concealment. The statistician will then match these numbers to the pre-generated allocation sequence and relay the assigned allocations back to the trial manager. The trial statistician and health economist will remain formally blinded to group allocation until the analysis begins.

Other members of the research team will not be formally blinded, as they may need to access participant data or may inadvertently learn group allocations. For example, green providers may report participant engagement using names (since they lack access to participant identifiers), such as noting if a participant spends intervention sessions on their phone rather than engaging in activities. Additionally, if participants contact the research team to enquire about their group allocation, their names will be recognised alongside their assigned group.

To maintain confidentiality, names, contact details, and participant identifiers will be stored separately and held by the trial manager. Access to these details will be granted only when necessary, such as in cases where a participant poses a risk to themselves or others and needs to be withdrawn from the trial.

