# Planned Data Analysis

# Quantitative Data

A full statistical analysis plan will be specified and signed off in advance of data lock.

A CONSORT diagram will be used to describe the participant flow through the trial, with counts and percentages of those recruited and retained in the study (Eldridge et al 2016).

Characteristics related to feasibility of the trial will be reported with 95% confidence intervals, including: the percentage of screened people that are eligible, the percentage of screened people that are recruited, the number of people recruited per location per week, the percentage of participants that provide follow-up data, the percentage of intervention arm participants that attend at least 4 of the 6 nature-based sessions and the percentage of participants that complete each outcome measure. Characteristics of the study participants will be summarised using means and standard deviations (or medians and interquartile ranges) for continuous variables, and numbers and percentages for categorical variables.

As this is a pilot study, estimating intervention effectiveness is not a key objective. However, its potential impact on the mental health and wellbeing outcomes at follow-up will be estimated. Trial arms will be compared using mixed ("multilevel") linear regression models. These models will account for the correlation between the responses of intervention arm participants within the group (cluster). Satterthwaite's degrees of freedom correction will be applied to account for the small number of clusters in the analysis. If there are convergence problems, ordinary linear regression models will be fitted instead. The comparisons will be adjusted for the baseline score of the outcome. Adjusted mean differences between the trial arms and two-sided 95% confidence intervals will be reported; no hypotheses testing will be undertaken. No subgroup analyses will be undertaken.

To calculate intervention costs, the resource used for training and delivering the intervention (preparation, delivery, travel time) will be collected from the trainers and service managers, and nationally applicable unit costs will be applied.

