# Data collection, entry, coding and checking processes

#### Ouantitative data

Data management, coding, and checking will be carried out by the research team in accordance with legal requirements and the data management and research governance procedures of the University of Exeter. Personal data will be stored only as long as necessary after the study concludes, and with participants' consent, we aim to provide a summary of our findings within six months of the study's completion. Data generated from the study will be securely archived on password-protected University of Exeter servers for 10 years. Due to the small sample size of this pilot RCT, there is a risk that sharing data could compromise participant confidentiality. Additionally, we do not have the resources to facilitate data sharing in a way that ensures anonymity. As a result, we will not be making the dataset publicly available.

Nature-based providers will record participant attendance for each session using a prespecified data collection tool.

All participant questionnaires will be completed online using formats that are accessible using a smart phone. If participants are unable to complete the online forms, then paper copies can be sent with a stamped addressed envelope for return. These will be collected at three time points – at baseline (T0), after the 6-week intervention (T1) and after a further 6 weeks follow up (T2). These data will be finalised and analysed by the research team, including the statistician and health economist.

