# **Potential Bias**

Bias	Description	Risk	Mitigation
Selection bias	Possible underrepresentation	Medium	Multiple routes of
	of participant groups (e.g.		recruitment.
	ethnicity, gender, age etc).		Inclusive imagery and
	Maybe due to demographics		language on recruitment
	of local populations,		tools and websites.
	inequities in access to		Nature-based providers from
	services, perceptions of who		different localities.
	nature-based activities are for,		Waitlist control group
	recruitment modes,		
Observation	Inability to blind participations	Medium	Statements on recruitment
bias	to their allocated study arm –		material that effectiveness
	intervention group may score		evidence is currently lacking.
	more favourably at follow up.		
Attrition bias	Higher withdrawal from	Medium	Clear description of the trial
	control group due to not		and randomisation in the
	receiving the nature-based		information sheets.
	intervention		Offering chance to take part
			in nature-based activities
			after a waiting period.

			Communication with the control group throughout the trial period.
Detection bias	Research team influences assessments due to knowing allocation.	Low	Blinding of analysts until detailed data plan finalised.
Contamination	Additional nature-based activities undertaken by the control group.		Focus groups and participation surveys will assess participants engagement with nature outside of the intervention

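### The protocol calls the trial statistician blinded until analysis, but has that statistician match participant numbers to arms for every batch

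*Protocol*

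**What the plan says.** All but three of the relevant statements are in the Protocol section Randomisation and Blinding/Allocation Concealment.

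- On set-up: "The randomisation process will be set up and tested by the trial statistician".
- For each batch, "the trial manager will provide the statistician with a list of unique, non-identifying participant numbers to maintain allocation concealment".
- Then: "The statistician will then match these numbers to the pre-generated allocation sequence and relay the assigned allocations back to the trial manager".
- The next sentence: "The trial statistician and health economist will remain formally blinded to group allocation until the analysis begins".
- On everyone else: "Other members of the research team will not be formally blinded, as they may need to access participant data or may inadvertently learn group allocations".

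The Potential Bias table rates detection bias as low and lists one mitigation: "Blinding of analysts until detailed data plan finalised". The quantitative part of the section on data collection, entry, coding and checking says who does the analysis: "These data will be finalised and analysed by the research team, including the statistician and health economist". Planned Data Analysis gives the latest date for the analysis plan: "A full statistical analysis plan will be specified and signed off in advance of data lock".

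**The concern.** A person who looks up each participant number in the allocation sequence and reports the resulting arm knows the allocation. The protocol gives this task to the trial statistician and then describes the same person as blinded. The statistician is a named analyst, so this is one of only two people to whom the blinding claim applies.

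What is at stake is an assurance more than an estimate. Blinding an analyst is meant to show that the analysis plan and the data-handling decisions were settled without knowledge of arm. If the process runs as written, the trial report would claim that safeguard for the statistician while its own description of randomisation shows that it was absent. The Potential Bias table carries the same claim forward as its sole entry against detection bias.

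**Working it through.** There is no stated figure to reproduce. The check is a comparison of the text, plus one count.

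**Step 1: what the statistician handles.** The inputs are three locations, two batches per location, and 14 participants per batch with seven to each arm (Randomisation and Blinding/Allocation Concealment).

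- Allocations passing through the statistician: 3 × 2 × 14 = 84, the whole planned sample.
- Per arm: 3 × 2 × 7 = 42, which agrees with the Trial Summary.

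If batches go ahead at the stated minimum of twelve, the count is 3 × 2 × 12 = 72. That is still every participant.

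**Step 2: whether the participant numbers blind the statistician.** They are described as unique and non-identifying, and the stated purpose is allocation concealment. That hides who the person is. It does not hide which arm a number received from the person who assigns it.

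**Step 3: whether the number could later connect to outcomes.** Data protection and confidentiality says that contact details are held apart from the research data and joined through a unique ID. Planned Data Analysis links attendance, postcode and deprivation data through a unique identifier code. It is a reasonable inference, though not stated outright, that the number used at randomisation also labels the outcome records.

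**Step 4: whether the protocol contains anything that would restore the blinding.** Three arrangements could do so.

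- *Masked arm codes with the key held elsewhere.* None is described. The text speaks of the assigned allocations going back to the trial manager, and under Consent participants are told their arm by email.
- *A second statistician or another person doing the matching.* None is described. The only other statistician mentioned is the independent member of the Trial Steering Committee, who has no randomisation task.
- *An independent randomisation service.* None is described.

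**Step 5: who else the blinding covers.** The health economist is the only other person named as blinded. Nothing in the matching step gives the health economist any allocation. The rest of the team is expressly not formally blinded.

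**Step 6: when blinding ends.** One section ends it when analysis begins, the other when the detailed plan is final. These can be different dates, and the protocol does not say which governs.

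**The case against.** The strongest reply is that little depends on this, and much of that reply stands.

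- Detection bias in the table is described as the research team influencing assessments. The outcomes are self-reported online, and no section gives the statistician a part in helping participants complete them. Knowing the arm cannot alter a self-completed questionnaire.
- The main analysis leaves limited room for discretion. Planned Data Analysis names a mixed model with Satterthwaite's correction, ordinary linear regression if there are convergence problems, and adjustment for the baseline score. It excludes hypothesis tests and subgroup analyses.
- The primary objective concerns recruitment and retention rates, which are counts with confidence intervals.

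A reader might also infer three stronger things that the protocol does not support.

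- *That no blinding of analysts exists.* The health economist's blinding is untouched, so the failure is confined to the trial statistician.
- *That the statistician can watch outcomes by arm and steer open choices, including the outcome for the definitive trial.* Knowing which number is in which arm is not the same as having accumulating outcome data, and no section gives the statistician those data before lock. The sample size section bases the choice of primary outcome on completeness, score variability and participant feedback, none of which is a between-arm difference.
- *That signing off the analysis plan before data lock is itself an error.* It is a latest date, it is contradicted nowhere, and sign-off may come much earlier.

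What the reply does not remove is the conflict between two adjacent sentences. The protocol itself states both the process and the blinding claim, so a separate analysis plan cannot make them agree.

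**Conclusion.** The point holds for the trial statistician. As described, this analyst knows the arm of all 84 planned participant numbers from randomisation onwards, so the statement that the statistician is blinded until analysis is wrong, and the detection-bias mitigation does not cover this person. The health economist is not affected by this step.

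The practical effect on estimates is probably modest, for the reasons given above. The correction is still worth making because the claim would otherwise pass into the trial report, and possibly into the design of the definitive trial.

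The conclusion rests on two assumptions: that the matching is done as written, by the statistician and with real arms, and that no unstated masking or second person is involved. If such an arrangement exists in practice, describing it in the protocol would resolve the contradiction.

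**What to change.** Choose one of two routes.

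(a) *Make the claim true.* Have an existing team member, or a system, outside the writing of the analysis plan and the analysis generate or hold the final sequence and do the matching. For example, the statistician writes and tests the code, and another person runs it with a new seed, keeps the list and relays the allocations to the trial manager. The protocol should name the role that holds the sequence. If a system is used, it should still say who holds the list, because hiding a field does not blind someone who generated the sequence.

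(b) *Withdraw the claim.* State under Randomisation and Blinding/Allocation Concealment that the trial statistician is not blinded, and revise the mitigation in the Potential Bias table to cover only the health economist. In this case, sign off the analysis plan before the statistician receives any follow-up outcome data. This is a supporting safeguard to replace the lost one, not the correction of an error in the present timing.

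Under either route, give one end point for blinding in both sections.

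The cost is small. Route (a) takes a short handover and a little of another person's time for each of the six batches. Route (b) is a change of wording and, if needed, an earlier sign-off. Neither changes the sample size, the visits or the data collected.
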